3.5.2. Visit Schedule

A summary of the visit schedule and assessments is presented in [Table 2](#).

Table 2: Visit Schedule and Assessments

Treatment Period	Screening	Day 1 ^a (M)	Induction (Weeks 1-3)				Rest (Weeks 4-5)	Challenge (Week 6)				
			M 8, 15	Tu 2, 9, 16	Th 4, 11, 18	F 5. 12, 19		M 36	Tu 37	W 38	Th 39	F 40
Study Days												
Informed consent	X											
Inclusion/Exclusion	X	X										
Medical history	X											
Demographic information	X											
Fitzpatrick Skin Typing	X											
UPT		X										X
MED irradiation/evaluation		X ^b		X ^c								
Randomization		X										
Product application		X	X		X			X				
Application site evaluations		X	X	X	X	X ^d		X	X	X	X	X
Application site irradiation				X		X ^d			X			
Untreated control site irradiation									X			
Make-up evaluation/application							X ^e					
Make-up evaluation/irradiation							X ^e					
Review of concomitant medications	X	X	X	X	X	X	X ^f	X	X	X	X	X
Review of AEs	X	X	X	X	X	X	X ^f	X	X	X	X	X

a Screening and the first day of Induction (Day 1) may take place on the same day.

b MED irradiation on Day 1.

c MED evaluation on Day 2.

d Evaluations will not be conducted after irradiation on the last Friday of the Induction Phase.

e Make-up evaluation/application and evaluation/irradiation are performed as necessary (see [Section 3.5.1](#)).

f Concomitant medications and AEs will be reviewed only for subjects who are required to return to the test facility for make-up visits during Rest Period - Week 4.

Note: The visit schedule may be revised if necessary.

3.5.3. Definition of Minimal Erythema Dose

Minimal erythema dose is defined as the length (in time) of light exposure required to produce a minimal erythema reaction 16 - 24 hours after irradiation using a standardized filtered UV light source that emits UVA/UVB (full spectrum) irradiation as part of its emission spectrum.¹²

3.5.4. Light source

The light source will be a Xenon Arc Solar Simulator (150 W), with UV-reflecting dichroic mirror, UVC-blocking filter, and visible/infrared blocking filter to generate a continuous emission spectrum in the UVA and UVB range (290 to 400 nm).¹² An additional filter is added during irradiation of the 6 J/cm² of UVA (320-400 nm) to the test sites to block UVB radiation allowing only UVA irradiation of the sites. The output is measured daily prior to irradiation using a radiometer/photometer.

3.5.5. Background Information

Date of birth, gender, race, Fitzpatrick skin type (see [Table 1](#)), and a significant medical history of each subject will be recorded at Screening.

3.5.6. Efficacy Assessments

No efficacy will be assessed in this study.

3.5.7. Safety Assessments

3.5.7.1. Patch Test Site Evaluations

For both Induction and Challenge Phases, after 24 hours (± 4 hours) of product application, all sites will be evaluated, and one application site of each product and the additional untreated site will be irradiated. The sites will be examined for dermal reactions at approximately 24 hours, 48 hours, and 72 hours post-irradiation.

The scores in [Table 3](#) will be used to express the response observed at the time of examination and will be recorded on the subjects' CRFs. The score will be used for statistical analysis.

Additional response notations are presented in [Table 4](#). The same evaluator (where possible) should perform the assessment throughout (from Induction to Rechallenge) the study.

Table 3: Response Scores

Response	Symbol	Numerical Equivalent Score
Erythema		
No reaction	-	0
Mild, but definite erythema	+	1
Moderate erythema	++	2
Marked/severe erythema	+++	3
Edema		
No reaction	-	0
Mild, but definite edema	**	1
Definite edema with erosion/vesiculation	***	2

Table 4: Notations

Response/Comment	Notation
Hyperpigmentation	Hr
Hypopigmentation	Ho
Vesiculation	V
Papular response	p
Papulovesicular response	pv
Damage to epidermis: oozing, crusting, and/or superficial erosions	D
Itching	I
Spreading of reaction beyond patch study site (ie, reaction where material did not contact skin)	S
Follicular irritation with or without pustule formation (folliculitis)	f
Subject absent	X
Patch dislodged	PD
Not patched	NP
No reaction	0

The readings will be made under a standardized white light source.

The 3-week period of patch contact during the Induction Phase may result in tape-related irritation in some individuals. Tape related irritation will not be graded as an irritant response at the patch site but will be noted separately on the CRF.

The Investigator will assess the reactions seen during the Challenge Phase and determine whether the subject is photosensitized or not. The following guidelines are generally considered in this assessment. Not all observations of erythema and edema are associated with photosensitivity; only if erythema and edema are observed can a reaction be suspected of being a positive photosensitivity reaction. An increase in the intensity of the reaction over time further supports an assessment of photosensitivity. If reactions are observed at both the irradiated and non-irradiated study product sites (ie, if contact sensitization may have occurred), the reaction at the irradiated site upon Rechallenge must be at least one grade more intense than at the non-irradiated site for the reaction to be suspected of being a photosensitivity reaction (refer to [Section 3.5.7.1](#) for response scores and notations).

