Study Design:	During the 3-week Induction Phase, MC2-01 Cream and MC2-01 Vehicle, will each be applied 2 times per week (Monday and Thursday) to 2 sites on the infrascapular area of the back under semi-occlusive patch conditions for approximately 24 hours (\pm 4 hours). Minimal erythema dose (MED) irradiation will also be performed for each subject on Day 1. After approximately 24 hours (\pm 4 hours) patches are removed, all application sites will be evaluated, and one application site of each study product will be irradiated with 2 times the subject's MED using the full Xenon lamp spectrum. All sites will be evaluated post irradiation at approximately 48 hours later when irradiated on Tuesdays and 72 hours later when irradiated on Fridays. If a subject misses an irradiation session during the Induction Phase, an additional application of study product may be applied on the Monday of the rest period (week 4) and an additional irradiation approximately 24 hours (\pm 4 hours) after application has occurred. At Challenge, MC2-01 Cream and MC2-01 Vehicle will each be applied once to 2 naïve sites on the infrascapular area of the back under semi-occlusive patch conditions for approximately 24 hours (\pm 4 hours). After patch removal, all application sites will be evaluated, and one site of each test product will be irradiated with 6 J/cm ² of Ultraviolet A (UVA) followed by 0.5 times the subject's MED of UVA/Ultraviolet B (UVB). An additional untreated site will also be irradiated at Challenge and will serve as an untreated control. Each site, including the untreated control site, will be evaluated again at approximately 24 hours, 48 hours, and 72 hours following irradiation. A Rechallenge will be performed if a cutaneous response observed during the Challenge Phase indicates possible photosensitization or at the discretion of the Investigator.
Planned Sample Size:	50 evaluable subjects
Study Population:	Healthy adult male and female volunteer subjects
Investigational Products:	MC2-01 Cream MC2-01 Vehicle
Control:	An untreated irradiated control site.

Efficacy Evaluation Criteria:	Not applicable

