At the end of the Induction Phase, the subjects will enter a Rest Period of 10-17 days and then a Challenge Phase. One application/irradiation session may be missed during the Induction Phase. If a subject misses an irradiation session during the Induction Phase, an additional application/irradiation session will be scheduled the Monday of rest period (week 4).

At Challenge, each study product will be applied in an amount of 0.2 g to 2 naive sites once for approximately 24 hours (\pm 4 hours) under semi-occlusive patches. After 24 hours (\pm 4 hour) of product application, all sites will be evaluated, and one application site of each product and the additional untreated site will be irradiated. The sites will be examined for dermal reactions at approximately 24 hours (\pm 4 hours), 48 hours (\pm 4 hours), and 72 hours (\pm 4 hours) post-irradiation. A Rechallenge should be performed if a cutaneous response observed during the Challenge Phase indicates possible photosensitization or at the discretion of the Investigator.

The safety endpoints for this study are irritation responses during the Induction Phase, positive responses at Challenge (ie, reactions indicative of a sensitization response) and AEs.

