4.6.2. Photosensitivity

The determination of dermal photosensitization potential will be made by the Investigator based on specific scoring criteria derived from observations in the Challenge Phase of the study and confirmed in the Rechallenge Phase, if necessary. The incidence of photosensitization reactions will be summarized by frequency counts for each treatment. If photosensitization occurs, the 95% confidence interval for the proportion of subjects with photosensitization for each product will be calculated. Photosensitivity will not be determined by statistical methods.

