### **11.2.1. Population I**

Photosensitization potential for each test product site will be assessed only among subjects completing the Induction and Challenge Phases for that product. To be considered a complete case for a particular test product, a subject must have 6 applications/irradiation and no less than 11 **subsequent** readings during Induction, 10-17 days rest, and 1 application and at 3 post-irradiation evaluations during Challenge for that product. However, those subjects who demonstrate photosensitization, even though they have not completed all visits, will also be included in this population and will be evaluated. If subject's patch sites were discontinued because they were considered by the Investigator to be pre-photosensitized during Induction, this subject will not be included in this population for that test product.

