**Statistical Analysis Plan**

**MC2 Therapeutics**  
Protocol No. MC2-01-C10

Page X of Y

Table 14.2.1.3: Summary of Dermal Responses by Response Scores and Notations During Challenge

Population I  
(N=XXX)

Time Post-Irradiation	MC2-01 cream		MC2-01 vehicle		Untreated
	Irradiated	Non-Irradiated	Irradiated	Non-Irradiated	Irradiated
N Sensitized [1]	xx (xx.x)	xx (xx.x)	xx (xx.x)	xx (xx.x)	xx (xx.x)
0 hours, n (%)					
-0	xx (xx.x)	xx (xx.x)	xx (xx.x)	xx (xx.x)	xx (xx.x)
[24 hours, n (%)] to [72 hours, n (%)]					
Response Score					
(Sum of Erythema and Edema)					
0	xx (xx.x)	xx (xx.x)	xx (xx.x)	xx (xx.x)	xx (xx.x)
1	xx (xx.x)	xx (xx.x)	xx (xx.x)	xx (xx.x)	xx (xx.x)
1 Hr	xx (xx.x)	xx (xx.x)	xx (xx.x)	xx (xx.x)	xx (xx.x)
2	xx (xx.x)	xx (xx.x)	xx (xx.x)	xx (xx.x)	xx (xx.x)
etc.	xx (xx.x)	xx (xx.x)	xx (xx.x)	xx (xx.x)	xx (xx.x)

[1] Sensitization classification made by the PI based on Challenge and Re-challenge

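### The plan does not define the photosensitization status of a subject who reacts at both sites of a product and has no completed Rechallenge, and its written guideline leans toward 'No'

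*Protocol*

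**What the plan says.** **Who decides.** Protocol 3.5.7.1 gives the decision to the Investigator: "The Investigator will assess the reactions seen during the Challenge Phase and determine whether the subject is photosensitized or not". It introduces its criteria with "The following guidelines are generally considered in this assessment". Both erythema and edema are needed before a reaction can be suspected. If both sites of a product react, suspicion carries a further condition: "the reaction at the irradiated site upon Rechallenge must be at least one grade more intense than at the non-irradiated site".

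**When Rechallenge happens.** Protocol 3.1, repeated in 3.5.1, states: "A Rechallenge should be performed if a cutaneous response observed during the Challenge Phase indicates possible photosensitization or at the discretion of the Investigator". The Synopsis is firmer: "A Rechallenge will be performed if a cutaneous response observed during the Challenge Phase indicates possible photosensitization", again with Investigator discretion as an alternative. Rechallenge patches go on once the Challenge reactions have resolved (3.5.1).

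**What the classification rests on.** Protocol 4.1 and SAP 11.8 base the diagnosis on the Investigator's review of responses after Challenge. Protocol 4.6.2 bases the determination on Challenge observations, "confirmed in the Rechallenge Phase, if necessary", and SAP 11.8 repeats this. The footnote to SAP Tables 14.2.1.3 and 14.2.1.4 and Listing 16.2.6.3 reads "Sensitization classification made by the PI based on Challenge and Re-challenge". SAP 11.1 refers back to the protocol for the working criteria.

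**Who is counted.** Population I (SAP 11.2.1) needs six applications with irradiation, at least 11 Induction readings, the rest period, and "1 application and at 3 post-irradiation evaluations during Challenge for that product". It also admits subjects who demonstrate photosensitization without having completed all visits. Completion of Rechallenge is not a requirement. Listing 16.2.6.3 records photosensitization as Yes or No, and SAP 8 rules out imputation.

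**The concern.** A both-site reactor is the hard case in this design. The reaction may be irritant, contact allergic or photoallergic, and the irradiated versus non-irradiated comparison is what separates them. The guideline places that comparison at Rechallenge and makes it a condition for suspicion, not only for confirmation. A subject whose irradiated site was clearly stronger at Challenge could decline Rechallenge, be lost, or not be selected for it. The written criterion could then not be met, however marked the difference at Challenge.

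The Investigator's count answers the primary objective. In a study of 50 subjects a single classification separates no cases from some. It also decides whether an interval is reported at all, because Protocol 4.6.2 plans one only if photosensitization occurs. A default toward 'No' favours a conclusion of no photoallergic potential, the less cautious direction for a safety study. Adverse event reporting is no backstop, because responses that can be scored on Tables 3 and 4 are not treated as AEs (Protocol 3.6.1 and 3.6.6).

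**Working it through.** **Step 1. Follow one subject through the text.** Take a subject with erythema and edema at the irradiated Challenge site of a product, a weaker reaction at its non-irradiated site, and no completed Rechallenge.

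1. *Suspected under 3.5.7.1?* The both-site criterion refers to the reaction at Rechallenge. There is none, so read literally the criterion is not met.
2. *Was Rechallenge called for?* Under the Synopsis, 3.1 and 3.5.1 it was, if Challenge indicated possible photosensitization. For a both-site reactor, 3.5.7.1 defers that very judgement to Rechallenge. The remaining route is Investigator discretion.
3. *Can Rechallenge be missing even when called for?* Yes. Subjects may leave at any time (3.3.3), and Rechallenge has no column in the visit schedule (Table 2).
4. *In the denominator?* Yes, if the other Population I requirements are met.
5. *What is recorded?* Yes or No. There is no third option and no rule for this subject. Under the footnote the classification draws on Challenge and Rechallenge. Under Protocol 4.1 and SAP 11.8 it can rest on responses after Challenge.

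No section states the outcome. The literal guideline points to 'No', and the Investigator's authority allows 'Yes'.

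**Step 2. Size.** The plan has no figure to reproduce. Fifty evaluable subjects is justified by convention, with no assumed rate, power or precision (Protocol 4.2, SAP 11.9).

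Inputs: n = 50 (Protocol 4.2). Assumed: all 50 are in Population I for the product, there are one or two unresolved subjects and no other case, and limits are exact two-sided 95% Clopper-Pearson. Protocol 4.6.2 names no interval method.

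- x = 0: the lower limit is 0. The upper limit is 1 − 0.025^(1/50) = 0.0711.
- x = 1: the lower limit is 1 − 0.975^(1/50) = 0.0005. The upper limit solves (1 − p)^50 + 50p(1 − p)^49 = 0.025, giving p = 0.1065.
- x = 2 and the n = 49 case use the same definition.

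| Handling | Count | Incidence | Exact 95% CI |
|---|---|---|---|
| One unresolved subject recorded No | 0/50 | 0% | 0 to 7.11% |
| One unresolved subject recorded Yes | 1/50 | 2.0% | 0.05 to 10.65% |
| One unresolved subject set aside | 0/49 | 0% | 0 to 7.25% |
| Two unresolved subjects recorded Yes | 2/50 | 4.0% | 0.49 to 13.71% |

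Each such subject moves the estimate by 1/50 = 2 percentage points. The first moves the upper limit by 10.65 − 7.11 = 3.54 points. Under Protocol 4.6.2 as written, the 0/50 result would carry no interval.

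**The case against.** The strongest reply is that a reader might infer a fixed rule, that a both-site reactor without Rechallenge is counted as a non-case, and the documents contain no such rule. The criteria are guidelines, the Investigator decides from the Challenge reactions, SAP 11.8 lets the diagnosis rest on responses after Challenge, and Rechallenge is confirmation where needed. This is right. Non-case status is the likely default, not an assigned one.

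The loop is also not closed. Investigator discretion can start a Rechallenge, and 3.5.1 gives its purpose as separating photosensitization from irritation, which fits a both-site reaction. A subject with a much stronger irradiated site is the one most likely to be sent on, and the Synopsis then makes Rechallenge firm. Nor does Population I require only a completed Challenge. It has Induction and rest requirements, and it retains subjects who demonstrate photosensitization with visits missing.

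The data would not be hidden either. Listing 16.2.6.3 shows each subject's irradiated and non-irradiated scores beside the classification. Finally, counting every such subject as photosensitized would override a diagnosis that the plan reserves to the Investigator, and Protocol 1.1.2 names skin irritation as a known effect of calcipotriene.

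All of this limits the claim but does not supply the missing rule. Discretion allows two subjects with identical scores to be classified differently. The score-frequency tables do not identify the unresolved reactor. The statements on the basis of classification still disagree.

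**Conclusion.** The point holds as an undefined classification with a lean toward 'No', and as an inconsistency between Protocol 3.5.7.1, the Rechallenge trigger, Protocol 4.1 and 4.6.2, SAP 11.8 and the table footnotes. It does not hold as a demonstrated bias. The documents do not say that such subjects are negative, and nothing in them shows how many there would be or that reactors would tend to refuse re-exposure.

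With one such subject and no other case among 50, the reported result is 0% with an upper limit of 7.11%, or 2.0% with an upper limit of 10.65%. The number of such subjects and the interval method are assumptions. With no such subject there is no effect. The documents list positive Challenge responses as a safety endpoint. The count bears on the primary objective, but they do not call it a primary incidence endpoint. The plan should settle the matter before treatment codes are merged.

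**What to change.** 1. **Reconcile the text.** Bring Protocol 3.5.7.1 into line with the Synopsis, 3.1, 3.5.1, 4.1 and 4.6.2, SAP 11.8 and the footnotes to Tables 14.2.1.3, 14.2.1.4 and Listing 16.2.6.3. The basis for calling a reaction suspected at Challenge and confirmed at Rechallenge should be the same everywhere. Who is rechallenged remains for the sponsor and the Investigator to settle.
2. **Keep the Investigator's diagnosis as the main count.**
3. **Add an 'unresolved' category** to Listing 16.2.6.3 and Tables 14.2.1.3 and 14.2.1.4. It covers subjects with erythema and edema at a product's irradiated Challenge site, at least one grade more intense than at that product's non-irradiated site, and no completed Rechallenge. The SAP should say whether a grade means the erythema score or the erythema-plus-edema sum.
4. **Report the incidence per product twice**, with unresolved subjects as non-cases and as cases, each with an exact 95% CI, including when the count is zero.

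The cost is a clarifying protocol sentence, a short SAP addition, and one row or field in each output. No new data are needed. The drawback is that the upper figure may include some irritant reactions, which is why it stands beside the Investigator's count and does not replace it.

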3.6. Adverse Events

3.6.1. Method of Determining Adverse Events

Safety assessments will include recording AEs reported spontaneously by the subject or collected by the Investigator. Adverse events will be collected during the period from the time of the signature of the informed consent form and first trial-related activity performed until the end of the trial. Adverse events will be recorded at each visit throughout the study on the appropriate CRF. Every attempt should be made to describe the AE in terms of a diagnosis. If a clear diagnosis has been made, individual signs and symptoms will not be recorded unless they represent atypical or extreme manifestations of the diagnosis, in which case they should be reported as separate events.

Subjects should be asked whether, since the time of the last observation or visit, they had any of the following:

- Experience any changes in well-being;
- Used any new medications other than those permitted in the inclusion criteria;
- Changed medication regimens (both prescription and OTC); and/or
- Were admitted to a hospital or had any accidents.

All questions should be of a general nature and should not suggest symptoms.

When an AE is suspected, all relevant evaluations will be carried out and appropriate treatment provided. Additional follow-up will be done as necessary ([Section 3.6.4](#)) and recorded in the subject's source documents, and the results will be provided to the Sponsor.

For AE definitions and reporting requirements refer to [Section 3.6.2](#) and [Section 3.6.3](#).

Note: Any observed response which can be denoted using the irritation criteria summarized in [Table 3](#) and [Table 4](#) will not be considered an AE. Likewise, any tape-related irritation will only be noted as an AE when all patches are discontinued due to tape reaction around all sites (see [Section 3.6.6](#)).

3.6.2. Adverse Event Definitions

3.6.2.1. Adverse Events

Information about all local and systemic AEs, whether volunteered by the subject, discovered by Investigator questioning, or detected through other means, will be collected and recorded on the AE CRF and followed as appropriate.

An AE is defined as any untoward medical occurrence in a patient or clinical investigation subject administered a pharmaceutical product (or cosmetic product), which does not necessarily have a causal relationship with this treatment. An AE can therefore, be any unfavorable and unintended sign, symptom, or disease temporally associated with the use of a medicinal IP, whether or not considered related to the medicinal IP.

Any AE that is considered related to the IP must be followed by the investigator until it is resolved or until the medical condition of the subject is stable; all relevant follow-up information will be reported to MC2 or designee. Adverse Events will be coded using the Medical Dictionary for Regulatory Activities (MedDRA).

Medical conditions/diseases present before starting study treatment are considered AEs only if they worsen after starting study treatment (any study procedures specified in the protocol). Any AEs occurring before starting study treatment but after signing the ICF are recorded on the Medical History/Current Medical Conditions CRF.

To the extent possible, each AE will also be described by:

1. its duration (start and end dates),
2. the severity grade (mild, moderate, severe)
3. its relationship to the study drug,
4. the action(s) taken, and
5. as relevant, the outcome.

Note: Any observed response which can be denoted using the irritation criteria summarized in [Table 3](#) and [Table 4](#) will not be considered an AE. Likewise, any tape-related irritation will not be noted as an AE.

The outcome of an AE will be classified as recovered, recovered with sequelae, recovering/resolving, ongoing, or death.

